STUDY PROTOCOL:

IMPROVING MENTAL HEALTH AND QUALITY OF LIFE OF PERSONS AFFECTED BY LEPROSY OR BURULI ULCER IN SOUTHERN NIGERIA.

Principal Investigator: [name]

German Leprosy and Tuberculosis Relief Association (GLRA), [name].

Funder: Leprosy Research Initiative

Project Duration: (4years) - 01 July 2020 to 30 June 2024

SUMMARY

Background

In Nigeria, leprosy and Buruli ulcer (BU) patients often lack access to mental health services. This gap in the National Tuberculosis and Leprosy Control Programme affirms the need to explore sustainable ways to make mental health services accessible to those in dire need.

This protocol describes a study in which we will determine the effect of using community lay counsellors, self-help groups of patients and trained frontline health workers in reducing mental disorders (especially, depression and anxiety disorders) and improving quality of life of persons affected by leprosy or BU.

Methods

A cluster randomized controlled study design will be employed. The study will involve persons affected by leprosy or Buruli ulcer. Ten local government areas (clusters) with the highest number of notified leprosy or BU cases between 2014 and 2018 in southern Nigeria will be purposively selected. The clusters will be randomized into intervention and control groups by using a computer-generated list of random numbers. At baseline, data on depression will be collected using Patient Health Questionnaire-9 (PHQ-9); generalized anxiety disorders using Generalized Anxiety Disorders-7 (GAD-7), self-stigma using Stigma Assessment and Reduction of Impact (SARI) scale and quality of life using WHOQOL-BREF and Warwick-Edinburgh Mental Well-being Scale

(WEMWBS) among eligible persons affected by leprosy or BU. The intervention will last for two years and will involve the use of community lay counsellors, self-help groups and training of frontline health workers in reducing mental disorders and improve quality of life among persons affected by leprosy/BU.

Discussion

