Mental health services in Nigeria are deficient in quantity and quality. It is estimated that there is currently one psychiatrist to one million inhabitants and 40:1,000,000 for psychiatric nurses. [21] Furthermore, distribution of the available professionals is grossly skewed in favour of urban areas. The organization of mental health services is top-heavy; at the apex of the pyramid are 8 federal neuro-psychiatric hospitals and about 20 departments of Psychiatry at University Teaching Hospitals. Referral systems are cumbersome and not patient-friendly. Health workers at the secondary and primary levels including Doctors and Nurses have little practical training in or awareness of mental health issues. This leaves majority of rural dwellers who constitute majority of the population underserved. The notion of universal coverage and the Sustainable Development Goal mantra of 'leaving no one behind' will remain unattainable if these circumstances persist.

Study design

This is a cluster-randomized trial involving ten LGAs with the highest number of notified leprosy or BU cases between 2014 and 2018, purposively selected from 220 LGAs in south-east/south-south Nigeria. Five LGAs namely, Ebonyi, Ogoja, Ogbaru, Ogbia and Calabar South were randomized as intervention LGAs and five comparable LGAs – Etinan, Ethiope East, Obubra, Anambra East and Isoko South will serve as control. For allocation of clusters (LGAs) to intervention and control groups, a computer-generated list of random numbers was used.

Baseline survey will be done in the first year of the project in both intervention and control LGAs to determine the magnitude of depression using Patient Health Questionnaire-9 (PHQ-9); generalized anxiety disorders using Generalized Anxiety Disorders-7 (GAD-7), self-stigma using Stigma Assessment and Reduction of Impact (SARI) scale and quality of life using WHOQOL-BREF and Warwick-Edinburgh Mental Well-being Scale (WEMWBS) among eligible persons affected by leprosy/BU.

Attitude of health workers and community leaders towards leprosy/BU patients will be assessed using Focus Group Discussions (FGDs) and Key Informant Interviews (KII). Additionally, social distance scale (SDS) will also be used for community leaders.

Intervention

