Two research assistants per LGA comprising members of the selected communities will be trained for one day for data collection using the interviewer administered questionnaire. The research assistants must have attained at least secondary education. They will be trained on privacy and confidentiality before the study begins. The researchers will conduct the FGDs and KIIs. Interviewers will be trained on confidentiality procedures and undertake to ensure confidentiality as part of their engagement agreement.

A secured box will be made available in German Leprosy and TB Relief Association head office for the safe storage of the questionnaires and other materials related to the research. The recordings used for FGDs and KIIs will be transcribed immediately after the interview. English, Pidgin English, Efik or Igbo languages will be used to conduct FGDs and the discussions will take place in secluded areas of the selected communities like public primary schools and town halls.

Data entry and analysis for (quantitative data collection method) will be done using IBM Statistical Package for Social Sciences (SPSS) statistical software version 25. Categorical variables among the study and control groups will be compared using Chi square test of statistical significance while continuous variables will be compared using Student t test. In between group comparisons (like study group before and after intervention) will be done using Mcnemar Chi square test for categorical variables and the dependent Student t test for continuous variables. In determining predictors of the outcome variables, independent variables that have a p value of less than 0.2 on bivariate analysis will be entered into the logistic regression model. The result of the logistic regression analysis will be reported using adjusted odds ratio and 95% confidence interval and the level of statistical significance will be determined by a p value of <0.05.

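### Ten LGAs are randomised, but the arms are compared with person-level chi-square and t tests that ignore clustering, so the 5% error rate is not held

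*Protocol*

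**What the plan says.** The Methods part of the Summary states that "A cluster randomized controlled study design will be employed". The Study design section repeats it: "This is a cluster-randomized trial involving ten LGAs with the highest number of notified leprosy or BU cases between 2014 and 2018". It names the intervention clusters: "Five LGAs namely, Ebonyi, Ogoja, Ogbaru, Ogbia and Calabar South were randomized as intervention LGAs". The control arm consists of five other named LGAs, described as comparable. On the mechanism it says: "For allocation of clusters (LGAs) to intervention and control groups, a computer-generated list of random numbers was used".

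The Data management section then fixes the quantitative analysis. Between arms, "Categorical variables among the study and control groups will be compared using Chi square test of statistical significance". Student t tests are named for the continuous outcomes. Before/after comparisons within a group use McNemar and paired t tests. Predictors of outcome are examined by logistic regression, with adjusted odds ratios and 95% confidence intervals. The decision rule is that "the level of statistical significance will be determined by a p value of <0.05".

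No section mentions an ICC, a design effect, LGA-level summaries, a random effect, GEE or cluster-robust standard errors.

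**The concern.** The unit of randomisation is the LGA, so the trial has ten randomised units, five against five. The chi-square test, the Student t test and ordinary logistic regression all assume that patients are independent. Within an LGA they are not. Two locally recruited research assistants per LGA administer the questionnaires in both arms, and patients in an LGA share the same community attitudes and health facilities. In intervention LGAs they also share lay counsellors, trained health workers and self-help groups averaging 15 persons.

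When outcomes are correlated within LGAs, the person-level tests understate the variance of the difference between arms. A difference that reflects only which LGAs fell into which arm can then pass the p<0.05 rule. The protocol says that a successful model will be integrated into the national programme and scaled up nationwide, so a false positive has practical consequences.

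**Working it through.** **Inputs from the protocol**
- Clusters: 10 LGAs, 5 per arm (Study design).
- Patients: 200 per arm, 30% anticipated loss (Sample size calculation). That is 200/5 = 40 per LGA, and 40 × 0.70 = 28 after loss.
- Prevalence: 50% (Sample size calculation), taken as the true value in both arms under the null hypothesis.
- Significance level: 0.05, taken as two-sided.

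**Assumptions not in the protocol**
- The ICC, shown from 0 to 0.10.
- Equal cluster sizes and the same ICC in both arms.

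**Formulas**
- Design effect: DE = 1 + (m − 1) × ICC, with m patients per LGA.
- Actual two-sided error of the person-level test at nominal 5%: 2 × [1 − Φ(1.96/√DE)].
- Example, m = 28 and ICC = 0.05: DE = 1 + 27 × 0.05 = 2.35; √DE = 1.53; 1.96/1.53 = 1.28; error = 20.1%.

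The formula was checked by beta-binomial simulation of 5 against 5 LGAs at 50% prevalence (40,000 runs).

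**The plan's own figure.** The stated 5% is reproduced only when patients are independent: at ICC 0 the simulated chi-square error is 4.9% (m = 28) and 5.0% (m = 40).

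**Actual type I error of the planned chi-square test**

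| ICC | DE, m=28 | Formula | Simulated | DE, m=40 | Formula | Simulated |
|---|---|---|---|---|---|---|
| 0.005 | 1.135 | 6.6% | about 6.4% | 1.195 | 7.3% | – |
| 0.01 | 1.27 | 8.2% | 7.9% | 1.39 | 9.6% | 9.9% |
| 0.02 | 1.54 | 11.4% | 11.2% | 1.78 | 14.2% | 14.3% |
| 0.05 | 2.35 | 20.1% | 19.8% | 2.95 | 25.4% | 25.7% |
| 0.10 | 3.70 | 30.8% | 31.2% | 4.90 | 37.6% | 38.2% |

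The Student t test on a continuous outcome, simulated with normal LGA effects (8,000 runs), behaves the same way. For ICC 0.01, 0.02, 0.05 and 0.10 the error is 8.2%, 12.0%, 20.4% and 32.5% with 28 per LGA. With 40 per LGA it is 9.4%, 13.4%, 24.8% and 37.8%.

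**Intervals.** A person-level standard error is too small by a factor √DE. With 28 per LGA that is √1.27 = 1.13 at ICC 0.01, √2.35 = 1.53 at 0.05 and √3.70 = 1.92 at 0.10.

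**Comparator.** A t test on the ten LGA proportions (8 degrees of freedom) rejected 5.0–5.4% of the time across all these settings.

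**Power of that valid test**, with 28 per LGA. The protocol's 35% reduction can be read as 50% falling to 32.5% or to 35%:

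| ICC | 50% vs 32.5% | 50% vs 35% |
|---|---|---|
| 0.01 | 65% | 52% |
| 0.02 | 57% | 45% |
| 0.05 | 41% | 32% |

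**The case against.** **The size is not known.** The protocol gives no ICC, and at 0.005 the error is only about 7%. This stands as a limit on size: the rate at least doubles only from an ICC of about 0.02. It does not rescue the plan, which is exact only at an ICC of zero, and nothing in the protocol supports zero.

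**Some sources of correlation exist in one arm only.** Counsellors and self-help groups belong to the intervention. True, but interviewers and local setting act in both arms. Even with clustering in one arm alone, the average DE at ICC 0.05 is (2.35 + 1)/2 = 1.675 with 28 per LGA, an error of about 13%. With 40 per LGA it is (2.95 + 1)/2 = 1.975, about 16%.

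**The tests might be meant for LGA means, or settled in a separate analysis plan.** A t test on ten LGA means would be valid, but the text never says so. Chi-square, McNemar and logistic regression point to individual records. The protocol names the tests itself, so this is not a detail left open.

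**The logistic regression is for predictors, not for the arm comparison.** This is a fair reading, and the only confidence interval that the analysis paragraph names is the one attached to that regression. It still assumes independent patients and needs the same correction, as do the before/after tests.

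**The LGAs may have been matched.** The Sample size calculation section refers to matched pairs and the controls are called comparable. The Study design section, however, describes allocation from a random list without pairing, so 8 degrees of freedom fit the text as it stands.

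**Conclusion.** The concern holds. The protocol randomises LGAs and fixes a person-level analysis, so the p<0.05 rule does not keep a 5% false-positive rate for any positive ICC. With 28 patients per LGA the true rate is about 8% at ICC 0.01, 11% at 0.02, 20% at 0.05 and 31% at 0.10. With 40 per LGA it is about 10%, 14%, 25% and 38%. Adding all eligible Buruli ulcer patients to the 400 leprosy patients enlarges the clusters and raises these figures.

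The figures rest on an assumed ICC, equal cluster sizes, equal ICCs in both arms and 50% prevalence. The direction of the error rests on none of these beyond some positive correlation within LGAs. Every between-arm comparison made with these tests is affected, including those for the primary objective, so the analysis must be corrected before the arms are compared.

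**What to change.** Rewrite the quantitative analysis paragraph in Data management so that every between-arm comparison respects the LGA as the randomised unit. Either approach below fits the design; with only ten clusters the first is the safer choice, and it is the one checked by simulation here.

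- **LGA-level analysis.** Compute one summary per LGA for each outcome and compare the five against five by a t test with 8 degrees of freedom. Support it with a permutation test over the C(10,5) = 252 possible allocations.
- **Mixed model.** Analyse individual data with a random LGA intercept and small-sample (Satterthwaite) degrees of freedom, which SPSS can fit.

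In the logistic regression, include LGA as a random effect. A fixed LGA effect cannot be separated from arm. Treat the before/after tests in the same way, and report the ICC with each result.

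State plainly whether the LGAs were matched before randomisation. If they were paired, a paired analysis is needed: 4 degrees of freedom, and 2⁵ = 32 allocations, for which the smallest two-sided permutation p-value is 2/32 = 0.0625.

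The cost is one rewritten paragraph and no new data. Intervals will be wider, and the valid analysis will probably fall short of the stated 80% power (65% at ICC 0.01 and 41% at 0.05 for 50% vs 32.5%, with 28 per LGA). The Sample size calculation section should therefore be revisited at the same time.

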- To determine the magnitude of mental disorders among persons affected by leprosy/BU in Southern Nigeria.
- 2. To determine the impact of a community-oriented, holistic approach on mental health status (depression and generalized anxiety disorder (GAD)) of persons affected by leprosy or BU.
- 3. To determine the impact of a community-oriented, holistic approach on quality of life of persons affected by leprosy or BU.
- 4. To determine the impact of a community-oriented, holistic approach on social participation of persons affected by leprosy or BU.
- 5. To determine the effect of socio-demographic variables on mental health status (depression and GAD) status of persons affected by leprosy or BU.
- 6. To determine the effect of physical impairment on mental health status (depression and GAD) of persons affected by leprosy/BU.
- 7. To determine the impact of a community-oriented, holistic approach on access to and utilization of mental health services and number of referrals for mental health care within all the levels of care.

Methodology

Nigeria, a West African country of nearly 200 million people is the most populous country in Africa. The country is divided into 36 States in 6 geopolitical zones and a Federal Capital Territory (FCT). Each state is divided into Local Government Areas (LGAs), which represent the third administrative level of governance. Altogether, there are 774 LGAs. The NTBLCP under the Federal Ministry of Health was inaugurated in 1988. The NTBLCP was initially responsible for Tuberculosis and Leprosy control but later added Buruli ulcer to its portfolio. At the turn of the century and up to 2007, Nigeria notified about 5,000 new leprosy cases annually. [17] Case notification declined steadily to 2687, 2447 and 2095 respectively in the last 3 years. Proportion of cases with visible deformities had remained high at 14-15%. Child and female proportion stood largely unchanged at 9% and 41% respectively. Despite achieving the WHO leprosy elimination target of less than 1 per 10,000 population in 1998, there continues to be pockets of high endemicity in some States and LGAs across the country.

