Community opinion leaders will serve as lay-counsellors for patients with mental health disorders. These may include religious leaders, school teachers, retired civil servants, youth and women leaders and other respected members of the community. At least five lay-counsellors will be selected per LGA.

The primary healthcare workers include nurses and community health officers(CHOs). They will work with community leaders to provide mental healthcare in form of pharmacotherapy and psychotherapy to diagnosed patients as well as ensure referral to psychiatrist/clinical psychologist whenever necessary. At least five healthcare workers will be recruited per LGA.

Inclusion criteria

- Any person affected by leprosy/BU
- All persons affected by leprosy/BU registered for treatment from 2014 up to one year before end of intervention.
- Participants aged between 15 to 65 years.

Exclusion criteria

- Refusal to give consent
- Patients who need urgent medical attention
- Patients unable to communicate clearly

Sample size calculation

A study in Nigeria revealed that 58% of leprosy patients have mental disorders. [4] This study anticipates that 50% of respondents will have mental disorders and 35% reduction is desired after intervention. A study demonstrated that training of community lay-workers could reduce prevalence of depression by more than 20%. [15] A World Bank study revealed 22% of Nigerians are depressed.[22] Therefore, sample size calculation for matched pairing at power=80%; p=0.05 and anticipated 30% loss to follow up is 400 leprosy patients (200 each group: intervention/control). Calculation was powered by leprosy alone, because data on mental disorders among BU patients are unavailable. However, it is known that many features (disfigurements and

stigma) known to result in mental health disorders are similar in both diseases. All eligible BU patients will be included.

2.5.6 Data collection methods:

Data will be collected from persons affected by leprosy/BU at baseline and post intervention and from community leaders and healthcare workers in intervention and control LGAs. Data collection tools include: PHQ-9, GAD-7, WEMWBS, SARI stigma scale, WHOQOL-BREF, SDS, FGD/KII guides, Log-books kept by community leaders and SHGs and registers for routine leprosy/BU data collection. Data will include:

- Bio-demographic information

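### A bivariate p<0.2 screen decides whether the exposures named in objectives 5 and 6 enter the logistic model, so physical impairment may get no adjusted estimate

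*Protocol*

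**What the plan says.** Two secondary objectives in the Protocol are about named exposures. Objective 5 reads "To determine the effect of socio-demographic variables on mental health status (depression and GAD) status of persons affected by leprosy or BU"; objective 6 reads "To determine the effect of physical impairment on mental health status (depression and GAD) of persons affected by leprosy/BU".

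The quantitative paragraph of the Data management section gives the only multivariable method for them. It opens with "In determining predictors of the outcome variables" and states the entry rule: "independent variables that have a p value of less than 0.2 on bivariate analysis will be entered into the logistic regression model". On output it says: "The result of the logistic regression analysis will be reported using adjusted odds ratio and 95% confidence interval". Terms in the model are then judged at the 5% level, with no allowance for the screening step.

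No variable is exempt from the screen. Neither impairment, nor the socio-demographic variables, nor any known confounder is kept in the model on subject-matter grounds.

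**The concern.** The objectives ask for the effect of a stated exposure. The analysis rule treats that exposure as one candidate predictor among many and lets its crude p-value decide whether it is modelled. Two things can go wrong.

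- **The exposure is lost.** If impairment gives a bivariate p of 0.2 or more, objective 6 has a crude result but no adjusted odds ratio. A crude association can be weak because a confounder works against it, and that is where adjustment is most needed.
- **A confounder is lost.** A variable that matters jointly but looks unimportant alone stays out, and the odds ratios that remain are adjusted for less than they should be.

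At stake is the answer to two secondary objectives. A report could say that impairment showed no independent effect when it was never in the model.

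**Working it through.** **Inputs from the Protocol**
- Exposure prevalence 15%. The Methodology section gives a national figure for notified leprosy cases: "Proportion of cases with visible deformities had remained high at 14-15" per cent. It stands in here for impairment in the study LGAs, which the Protocol does not give.
- Outcome prevalence 50% (Sample size calculation: "50% of respondents will have mental disorders and 35% reduction is desired after intervention").
- 400 leprosy patients, or 400 × 0.70 = 280 after the planned 30% loss.
- Screen at two-sided p<0.2, that is |z| > 1.2816; final test at 0.05.

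**Assumptions not in the Protocol:** odds ratios of 1.5 and 2, an exposure prevalence of 30% as an alternative, and the confounders used in step 3. Clustering is ignored.

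**1. Chance that a real effect fails the screen, no confounding.** At 50% in the unexposed, an odds ratio of 1.5 gives odds of 1.5, or 60%, in the exposed.
- n = 400: 60 exposed, 340 unexposed. SE = √(0.6×0.4/60 + 0.5×0.5/340) = 0.069; z = 0.10/0.069 = 1.45. P(|Z| < 1.2816) = 0.43.
- n = 280: the same formula gives 0.52.

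Simulation (2,000 runs, six other covariates) agrees. Share of trials in which impairment is dropped:

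| Odds ratio | Exposed | n=400 | n=280 |
|---|---|---|---|
| 1.5 | 15% | 44% | 54% |
| 1.5 | 30% | 28% | 39% |
| 2 | 15% | 13% | 23% |
| 2 | 30% | 3% | 10% |

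**2. Does that cost detections?** Not without confounding. The adjusted z is then close to the crude z, so a variable below 1.28 does not reach 1.96 after adjustment. At odds ratio 1.5, 15% exposed and n = 400, the fixed model was significant in 28.2% of runs and the screened model in 28.0%. In 0 of 1,500 runs was impairment screened out but significant in the fixed model, and again 0 of 1,500 at n = 280. What is lost here is the adjusted estimate and its interval, not a significant finding.

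**3. With an opposing confounder.** At odds ratio 2 and n = 400, impairment is dropped in roughly 20-45% of trials, and detection falls from 64-84% (fixed model) to 54-78% (screen). Stronger assumed confounding makes it worse. At 30% exposed, with a confounder coefficient of -0.4 to -0.6 on the log-odds scale and a correlation of 0.4 to 0.5, impairment is dropped in 28-67%. Detection is then 32-71% under the screen against 81-83% under the fixed model.

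**4. P-values and intervals for null variables.** Given entry, P(p<0.05 | p<0.2) ≈ 0.05/0.20 = 25%, and coverage of the 95% interval is about 1 − 0.25 = 75%. Simulation at odds ratio 1 without confounding gave 25-29% significant and 71-76% coverage. Counting dropped variables as non-significant, the rate over all trials is 0.20 × 0.25 = 5% (simulated 4.5-5.7%). For real effects of 1.5 to 2 without confounding, coverage given entry was 94-98%.

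**5. Is there room for a fixed model?** Take ten events per parameter as a guide.
- 400 × 0.50 = 200 events: about 20 parameters.
- If depression were as rare as the 22% that the Sample size calculation gives for Nigerians in general: 400 × 0.22 = 88 events, about 9 parameters.
- Endline, 280 patients at 50% and 35% (one reading of the target reduction): 140 × 0.50 + 140 × 0.35 = 119 events, about 12 parameters.

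Five terms (impairment, age, sex, education, disease) fit in every case if each takes one parameter. Nine LGA indicators would bring the total to 14, which fails the last two.

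**6. LGA and arm.** The Study design section allocates whole LGAs, five to each group. An intercept with nine LGA indicators has rank 10; adding arm leaves it at 10. Arm is then not estimable.

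**The case against.** The other side has several good arguments.

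- **Type I error.** A reader might infer that the rule breaks the 5% level and makes the reported inference invalid. It does not: over all trials the rate stays near 5%, and coverage for real, unconfounded effects is close to nominal. The 25% is conditional on entry and should not be set against an unconditional 5%. What stands is that the adjusted table shows only variables that entered, so null variables in it look significant too often.
- **Power.** A reader might infer that 44% of trials would miss a real effect because of the screen. Step 2 shows otherwise: without confounding, low power is the cause and a fixed model shares it. Lost detections need an opposing confounder, and the Protocol does not describe one.
- **Inputs.** The 15% is national, concerns leprosy and counts visible deformity only. The odds ratios are assumed, and at odds ratio 2 with 30% exposed the drop rate is 3%. The 400 excludes Buruli ulcer patients, all eligible ones of whom will be added, so the real sample is larger.
- **Scope.** The rule covers predictor analyses, and a crude impairment result must still be computed. A covariate list could sit in an SAP. However, the Protocol is not silent here: it states a selection rule that has no exception, and a crude figure is weakest where confounding is present.

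**Conclusion.** The point holds in limited form. The stated rule can leave the exposure named in objective 6 without an adjusted estimate, and can do the same to the variables in objective 5 and to confounders of either. How often depends on assumed effects: about 44% of trials at odds ratio 1.5 with 15% impaired and 400 patients, falling to 3% at odds ratio 2 with 30% impaired. Detections are lost only when a confounder opposes the effect; under the moderate confounding assumed, detection falls from 64-84% to 54-78%. Distortion of p-values and intervals is a matter of null variables that pass the screen.

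A reader might also infer that the trial's main result is at risk. The documents do not support that: the groups are compared by chi-square and t tests, to which the entry rule does not apply. This is a change that should be made for two secondary objectives.

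**What to change.** For objectives 5 and 6, replace the screen with one pre-specified logistic model each for depression and GAD. It contains physical impairment, age, sex, education and disease (leprosy or BU), all entered whatever their p-values. Report every odds ratio with its 95% interval. If a screened model is still wanted, label it exploratory.

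Account for LGA by a random effect or a cluster-level method. Do not enter LGA fixed effects together with study arm in endline models, because LGA determines arm.

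The cost is analysis wording only. The small downside is a few more parameters than a screened model would carry, which matters only if depression or GAD proves much less common than 50%.
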